**Table 15-1: Investigator Reports Applicable for all Geographies per Medtronic Requirements**

Report	Submit to	Description/Constraints
Final investigator report	Sponsor, IRB s and Relevant Authorities	This report must be submitted within 3 months of study completion or termination of the investigation or the investigator's part of the investigation. (21 CFR 812.150(a)(6))
Other	IRB and FDA	An investigator shall, upon request by a reviewing IRB, FDA or any other regulatory agency, provide accurate, complete, and current information about any aspect of the investigation. (21 CFR 812.150(a)(7))

## 15.9.2 Sponsor Reports

Medtronic shall prepare and submit the following complete, accurate, and timely reports listed in the tables below (by geography). In addition to the reports listed below, Medtronic shall, upon request of the reviewing IRB or FDA, provide accurate, complete and current information about any aspect of the investigation. Safety data Medtronic reporting requirements are listed in [Table 15-2](#).

**Table 15-2: Sponsor Records and Reporting Responsibilities**

Report	Submit to	Description/Constraints
Premature termination or suspension of the clinical investigation	Investigators, IRB Relevant authorities and Head of the Institution	Provide prompt notification of termination or suspension and reason(s). (ISO 14155:2020)
Unanticipated Adverse Device Effect	Investigators, IRB, FDA, and relevant authorities	Notification within ten working days after the sponsor first receives notice of the effect. (21 CFR 812.150(b)(1))
Withdrawal of IRB approval	Investigators, Head of Institution, IRB and relevant authorities	Investigators, IRBs will be notified only if required by local laws or by the IRB
Withdrawal of FDA approval	Investigators, Head of Institution, IRB, and relevant authorities	Notification within five working days after receipt of notice of the withdrawal of approval. (21 CFR 812.150(b)(3))
Investigator List	FDA	Submit at 6-month intervals, a current list of the names and addresses of all investigators participating in the investigation. (21 CFR 812.150(b)(4))
Progress Reports	IRB and RAs	Progress reports will be submitted at least annually. (21 CFR 812.150(b)(4)(5), 812.36(f))

*Medtronic Business Restricted*

**CONFIDENTIAL**

056-F275, vC Clinical Investigation Plan Template

# The Early Feasibility Study of the Intrepid™ TMVR Transseptal System Clinical Investigation Plan

Version 4.0

Page 68 of 102

Medtronic

**Table 15-2: Sponsor Records and Reporting Responsibilities**

Report	Submit to	Description/Constraints
Recall and device disposition	Investigators, IRB, relevant authorities, and FDA	Notification within 30 working days after the request is made and will include the reasons for any request that an investigator return, repair, or otherwise dispose of any devices. (21 CFR 812.150(b)(6))
Failure to obtain Informed Consent	FDA	Investigator's report will be submitted to FDA within five working days of notification. (21 CFR 812.150(b)(8))
Final report	Investigators, IRB, Regulatory authorities, and FDA	Medtronic will notify FDA within 30 working days of the completion or termination of the investigation. A final report will be submitted to the FDA, investigators, and IRBs within six months after completion or termination of this study. (21 CFR 812.150(b)(7))
Study deviation	Investigators	Ensure that all deviations from the CIP are reviewed with the appropriate clinical investigator(s), are reported on the CRFs and the final report of the clinical investigation. (ISO 14155:2020) Study site specific study deviations will be submitted to investigators periodically.

## 15.10 Publication and Use of Information

Medtronic is committed to the widespread dissemination of all primary and secondary endpoint results. A Publication Plan will be implemented and followed as indicated in the CTA.

A separate Publication Plan will provide detailed information about the publication committee, authorship, publication proposals, and requests for data.

## 15.11 Suspension or Early Termination

### 15.11.1 Planned Study Closure

Study Closure is a process initiated by distribution of a study closure letter. Study closure is defined as closure of a study that occurs when Medtronic and/or regulatory requirements have been satisfied per the CIP and/or by a decision by Medtronic or regulatory body), whichever occurs first. The study closure process is complete upon distribution of the Final Report or after final payments, whichever occurs last. Ongoing IRB oversight is required until the overall study closure process is complete.

*Medtronic Business Restricted*

**CONFIDENTIAL**

056-F275, vC Clinical Investigation Plan Template

### **15.11.2 Early Termination or Suspension**

Early Termination is the closure of a study that occurs prior to meeting defined endpoints. This is possible for the whole study or a single study site. Suspension is a temporary postponement of study activities related to enrollment and distribution of the product. This is possible for the whole study or a single study site.

**CONFIDENTIAL**

056-F275, vC Clinical Investigation Plan Template

**CONFIDENTIAL**

056-F275, vC Clinical Investigation Plan Template

## **17.0 Appendices**

### **17.1 Definition of Terms & Causal Relationships**

#### **17.1.1 ACCESS SITE AND VASCULAR COMPLICATIONS**

Access and vascular complications will be defined and classified according to the Mitral Valve Academic Research Consortium (MVARC); Clinical Trial Design Principles and Endpoint Definitions for Transcatheter Mitral Valve Repair and Replacement: Part 2: Endpoint Definitions; JACC, 2015 (14).

Access Site and Vascular Complications	
I. Vascular complications	
1.	Major access site vascular complications, including: 

1. Aortic dissection or aortic rupture, or

2. Access site-related† arterial or venous injury (dissection, stenosis, ischemia, arterial, or venous thrombosis including pulmonary emboli, perforation, rupture, arteriovenous fistula, pseudoaneurysm, hematoma, retroperitoneal hematoma, atrial septal defect‡), irreversible nerve injury, or compartment syndrome resulting in death; hemodynamic compromise; life-threatening, extensive, or major bleeding (MVARC bleeding scale); visceral ischemia; or neurological impairment, or

3. Distal embolization (nond cerebral) from a vascular source requiring surgery or resulting in amputation or irreversible end-organ damage, or

4. Unplanned endovascular or surgical interventions resulting in death; life-threatening, extensive, or major bleeding (MVARC bleeding scale); visceral ischemia; or neurological impairment

2.	Minor access site vascular complications, including: 

1. Access site arterial or venous injury (dissection, stenosis, arterial, or venous thrombosis including pulmonary emboli, ischemia, perforation, rupture, arteriovenous fistula, pseudoaneurysm, hematoma, retroperitoneal hematoma, atrial septal defect‡) not resulting in death; life-threatening, extensive, or major bleeding (MVARC scale); visceral ischemia; or neurological impairment, or

2. Distal embolization treated with embolectomy and/or thrombectomy not resulting in amputation or irreversible end-organ damage, or

3. Any unplanned endovascular stenting or unplanned surgical intervention not meeting the criteria for a major vascular complication, or

4. Vascular repair (via surgery, ultrasound-guided compression, transcatheter embolization, or stent-

II. Cardiac structural complications due to access-related issues	
3.	Major cardiac structural complications, including: 

1. Cardiac perforation* or pseudoaneurysm resulting in death, life-threatening bleeding, hemodynamic compromise, or tamponade, or requiring unplanned surgical or percutaneous intervention

4.	Minor cardiac structural complications, including: 

1. Cardiac perforation* or pseudoaneurysm not meeting major criteria

\* Including the left ventricle, left atrium, coronary sinus, right atrium, and right ventricle.

† May arise from the access procedure per se or complications from vascular closure devices.

‡ Meeting pre-specified criteria for a hemodynamically significant shunt, or requiring unplanned percutaneous or surgical closure.

### 17.1.2 ACUTE KIDNEY INJURY

Acute Kidney Injury (AKI) will be defined and classified according to the Mitral Valve Academic Research Consortium (MVARC); Clinical Trial Design Principles and Endpoint Definitions for Transcatheter Mitral Valve Repair and Replacement: Part 2: Endpoint Definitions; JACC, 2015 (14).

Definition and Stages of Acute Kidney Injury	
Definition	Maximal changes in sCr from baseline to 7 days post-procedure
Stages	
Stage 1	Increase in sCr to 150%–199% (1.50–1.99x increase vs. baseline), increase of $\geq 0.3$ mg/dl ( $\geq 26.4$ mmol/l) within 48 h, or urine output $<0.5$ ml/kg/h for $\geq 6$ h but $<12$ h
Stage 2	Increase in sCr to 200%–299% (2.00–2.99x increase vs. baseline) or urine output $<0.5$ ml/kg/h for $\geq 12$ h but $<24$ h
Stage 3	Increase in sCr to $\geq 300\%$ ( $\geq 3.0$ x increase vs. baseline), sCr of $\geq 4.0$ mg/dl ( $\geq 354$ mmol/l) with an acute increase of $\geq 0.5$ mg/dl (44 mmol/l), urine output $<0.3$ ml/kg/h for $\geq 24$ h, or anuria for $\geq 12$ h; patients receiving renal replacement therapy are considered stage 3 irrespective of other criteria
Adapted with permission from Kappetein et al. Updated standardized endpoint definitions for transcatheter aortic valve implantation: The Valve Academic Research Consortium-2 consensus document. J Am Coll Cardiol 2012;60: 1438–54.	

### 17.1.3 AORTIC REGURGITATION

Aortic regurgitation will be classified according to the 2008 Focused Update Incorporated into the ACC/AHA 2006 Guidelines for the Management of Patients with Valvular Heart Disease; JACC, 2008 (12).

Aortic Regurgitation			
	Mild	Moderate	Severe
Qualitative			
Angiographic grade	1+	2+	3-4+
Color Doppler jet width	Central jet, width less than 25% of LVOT	Greater than mild but no signs of severe AR	Central jet, width greater than 65% LVOT
Doppler vena contracta width (cm)	Less than 0.3	0.3–0.6	Greater than 0.6

*Medtronic Business Restricted*

**CONFIDENTIAL**

056-F275, vC Clinical Investigation Plan Template

# The Early Feasibility Study of the Intrepid™ TMVR Transseptal System Clinical Investigation Plan

Version 4.0

Page 74 of 102

Medtronic

Aortic Regurgitation			
	Mild	Moderate	Severe
Quantitative (cath or echo)			
Regurgitant volume (ml per beat)	Less than 30	30–59	Greater than or equal to 60
Regurgitant fraction (%)	Less than 30	30–49	Greater than or equal to 50
Regurgitant orifice area (cm  )	Less than 0.10	0.10–0.29	Greater than or equal to 0.30
Additional essential criteria			
Left ventricular size	--	--	Increased

## 17.1.4 AORTIC STENOSIS

Aortic stenosis will be classified according to the 2008 Focused Update Incorporated into the ACC/AHA 2006 Guidelines for the Management of Patients with Valvular Heart Disease; JACC, 2008 (12).

Aortic Stenosis			
Indicator	Mild	Moderate	Severe
Jet velocity (m/s)	Less than 3.0	3.0–4.0	Greater than 4.0
Mean gradient (mmHg)*	Less than 25	25–40	Greater than 40
Valve area (cm  )	Greater than 1.5	1.0–1.5	Less than 1.0
Valve area index (cm  / m  )	--	--	Less than 0.6

\* Valve gradients are flow dependent and when used as estimates of severity of valve stenosis should be assessed with knowledge of cardiac output or forward flow across the valve. Modified from the Journal of the American Society of Echocardiography, 16, Zoghbi WA, Recommendations for evaluation of the severity of native valvular regurgitation with two-dimensional and Doppler echocardiography, 777–802, Copyright 2003, with permission from American Society of Echocardiography (33).

## 17.1.5 ARRHYTHMIAS AND CONDUCTION SYSTEM DISTURBANCES

Arrhythmias and conduction system disturbances will be defined and classified according to the Mitral Valve Academic Research Consortium (MVARC); Clinical Trial Design Principles and Endpoint Definitions for Transcatheter Mitral Valve Repair and Replacement: Part 2: Endpoint Definitions; JACC, 2015 (14).

*Medtronic Business Restricted*

**CONFIDENTIAL**

056-F275, vC Clinical Investigation Plan Template

# The Early Feasibility Study of the Intrepid™ TMVR Transseptal System Clinical Investigation Plan

Version 4.0

Page 75 of 102

Medtronic

## Arrhythmias and Conduction System Disturbances

For emerging mitral valve procedures in which the frequency of major arrhythmias and conduction system disturbances is unknown, continuous rhythm monitoring for at least 48 h in the post-procedural period is recommended to maximize the detection of arrhythmias and conduction system disturbances.

Data elements to be collected for all patients should include:

- I. Baseline conduction abnormalities, paroxysmal or permanent atrial fibrillation (or flutter), ventricular arrhythmias, and the presence of permanent pacemaker and implantable defibrillators\*
- II. Procedure-related new or worsened cardiac conduction disturbance (including first-, second- [Mobitz I or Mobitz II], or third-degree AV block; incomplete and complete right bundle branch block; intraventricular conduction delay; left bundle branch block; left anterior fascicular block; or left posterior fascicular block, including heart block) requiring a permanent pacemaker implant; each subclassified as persistent or transient
- III. New-onset atrial fibrillation (or flutter)†
- IV. New-onset ventricular tachycardia or fibrillation
- V. Pacemaker or defibrillator lead dislodgement

Arrhythmias and conduction system disturbances are subclassified according to:

- I. The occurrence of hemodynamic instability
- II. Need for therapy including electrical/pharmacological cardioversion or initiation of a new medication (oral anticoagulation, rhythm, or rate control therapy)
- III. Need for new permanent pacemaker and/or defibrillator implantation, including the indication(s) and the number of days post-implant. For patients with defibrillators, the number of appropriate and

\* The type of permanent pacemaker should be recorded (e.g., single vs. dual chamber, biventricular).

† Which lasts sufficiently long to be recorded on a 12-lead electrocardiogram, or at least 30 s on a rhythm strip.

AV = atrioventricular

### 17.1.6 BLEEDING COMPLICATIONS

Bleeding complications will be further defined and classified according to the Mitral Valve Academic Research Consortium (MVARC); Clinical Trial Design Principles and Endpoint Definitions for Transcatheter Mitral Valve Repair and Replacement: Part 2: Endpoint Definitions; JACC, 2015 (14).

Major bleeding will be defined as any bleeding event requiring transfusion of  $\geq 4$  U of whole blood or packed RBCs.

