## **4.0 Objectives and Endpoints**

### **4.1 Objectives**

#### **4.1.1 Primary Objective**

The primary objective of the study is to evaluate the safety of the Intrepid™ TMVR System by assessing the nature, severity and frequency of complications associated with the delivery and/or implantation of the device.

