### **4.2 Study Endpoints**

#### **4.2.1 Primary Safety Endpoint**

The primary safety endpoint is implant, delivery or device related serious adverse events (through 30 days post-procedure).

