## Definition of Bleeding Complications

### II. Major

Overt bleeding either associated with a drop in the hemoglobin of  $\geq 3.0$  g/dl‡ or requiring transfusion of  $\geq 3$  U of whole blood or packed RBCs AND does not meet criteria of life-threatening or extensive bleeding.

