### III. Extensive

Overt source of bleeding with drop in hemoglobin of  $\geq 4$  g/dl‡ or whole blood or packed RBC transfusion  $\geq 4$  U within any 24-h period, or bleeding with drop in hemoglobin of  $\geq 6$  g/dl‡ or whole blood or packed RBC transfusion  $\geq 4$  U (BARC type 3b) within 30 days of the procedure.

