### Type 5b

Definite fatal bleeding. Overt bleeding, autopsy, or imaging confirmation.

\* Modified with permission from VARC-2 (29).

† “Overt” bleeding is defined by any of the following criteria being met: Reoperation after closure of sternotomy for the purpose of controlling bleeding; chest tube output  $>2$  l within any 24 h period,  $>350$  ml within the first post-operative hour,  $\geq 250$  ml within the second post-operative hour, or  $>150$  ml within the third post-operative hour; or visible bleeding from the vascular system either at or remote from the access/surgical site.

‡ Adjusted for the number of units of blood transfused (1 U packed red blood cells or whole blood is equivalent to 1 g/dl hemoglobin).

§ Modified from BARC.

BARC = Bleeding Academic Research Consortium; IV = intravenous; MVARC = Mitral Valve Academic Research Consortium; RBC = red blood cells; VARC = Valve Academic Research Consortium.

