## 17.1.23 ENDOCARDITIS

Endocarditis will be defined and classified according to the Mitral Valve Academic Research Consortium (MVARC); Clinical Trial Design Principles and Endpoint Definitions for Transcatheter Mitral Valve Repair and Replacement: Part 2: Endpoint Definitions; JACC, 2015 (14).

Any 1 of the following:

- Fulfillment of the modified Duke endocarditis criteria (described below), or
- Evidence of abscess, paravalvular leak, pus, or vegetation confirmed as secondary to infection by histological or bacteriological studies during an operation or autopsy.

Should be further subclassified by organism, and early (<1 yr) vs. late (≥1 yr)

Modified Duke Criteria
Definite endocarditis according to the Modified Duke Criteria includes: 

• Histologic and/or microbiologic evidence of infection at surgery or autopsy, or

• 2 major criteria, or

• 1 major criteria or 3 minor criteria, or

• 5 minor criteria

 Major and minor criteria are as follows:

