### Modified Duke Criteria

If only 1 major and 1-2 minor criteria are fulfilled, or if only 3-4 minor criteria are fulfilled, the event will be coded as "possible endocarditis"

Medtronic Business Restricted

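### Two event definitions in Appendix 17.1 of the Early Feasibility Study CIP contradict themselves: Major bleeding has two incompatible thresholds, and every endocarditis pattern coded as possible also qualifies as definite

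*Combined protocol and SAP*

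**What the plan says.** **Bleeding (EFS CIP 17.1.6).** The section refers bleeding to the MVARC scale and then adds its own sentence: "Major bleeding will be defined as any bleeding event requiring transfusion of" at least 4 U of whole blood or packed red cells. It gives no hemoglobin route and no time window. The table that follows has different grades:

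- Major: "Overt bleeding either associated with a drop in the hemoglobin of" at least 3.0 g/dl, or at least 3 U, provided the bleed is not extensive or life-threatening.
- Extensive: "Overt source of bleeding with drop in hemoglobin of" at least 4 g/dl, or at least 4 U, within any 24 h; or a drop of at least 6 g/dl, or at least 4 U, within 30 days of the procedure.
- A footnote says hemoglobin drops are "Adjusted for the number of units of blood transfused", with 1 U equal to 1 g/dl.

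**Endocarditis (EFS CIP 17.1.23).** Definite endocarditis is met by surgical or autopsy evidence, by 2 major criteria, by "1 major criteria or 3 minor criteria", or by 5 minor criteria. The end of the same table turns to cases with only 1 major and 1–2 minor criteria, "or if only 3-4 minor criteria are fulfilled, the event will be coded as" possible endocarditis.

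**Use.** The primary objective is "assessing the nature, severity and frequency of complications associated with the delivery and/or implantation of the device" (Section 4.1.1). Section 13.0 bases event definitions on MVARC and promises FDA event summaries for all subjects. Section 12.1 has the CEC adjudicate by the definitions in the protocol and its charter.

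**The concern.** A study whose primary objective is the severity and frequency of complications needs each event to have one grade. As printed, a 3 U bleed is Major in the table but not under the sentence. A 4 U bleed within 30 days is Major under the sentence and one grade higher in the table. A patient with one major and one minor Duke criterion is both definite and possible.

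The bleeding sentence may have been meant as a separate transfusion category, but it reuses the name of an MVARC grade and does not say so.

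What is at stake is the labels in the descriptive safety and event summaries, and any MVARC outcome that takes endocarditis from this appendix. Section 17.1.32 also lists major bleeding, with no scale named, among the conditions for cardiovascular death. That matters little, because the same list includes an open category for other cardiovascular causes.

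**Working it through.** The plan gives no figure to reproduce, so the check applies each rule as written to every combination of inputs. The cells have equal weight; they show where the rules disagree, not how often.

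**Bleeding: inputs and rules.** Overt bleeds, life-threatening criteria absent. Units *u* = 0–7 and measured drop *d* = 0–7 g/dl give 8 × 8 = 64 cells. The adjusted drop is *a* = *d* + *u* (footnote).

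- Sentence: Major if *u* ≥ 4.
- Table, Extensive: *a* ≥ 4 or *u* ≥ 4 in any 24 h; or, within 30 days of the procedure, *a* ≥ 6 or *u* ≥ 4.
- Table, Major: (*a* ≥ 3 or *u* ≥ 3) and not Extensive.

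The 24-h limit is assumed to apply to both the 4 g/dl drop and the 4 U, since otherwise the 6 g/dl line would be redundant. *Spread* means that no 24-h period reaches 4 U or an adjusted drop of 4 g/dl.

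| Timing | Major by table | Major by sentence | Both | Exactly one |
|---|---|---|---|---|
| Through day 30, all within 24 h | 4 | 32 | 0 | 36 |
| Through day 30, spread | 12 | 32 | 0 | 44 |
| After day 30, all within 24 h | 4 | 32 | 0 | 36 |
| After day 30, spread | 58 | 32 | 32 | 26 |

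How the counts arise:

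- Sentence: 4 unit values (4–7) × 8 drops = 32.
- All within 24 h: the table's Major needs *a* = 3 exactly, which is 4 cells. All have *u* ≤ 3, so none overlaps with the sentence: 4 + 32 = 36.
- Through day 30, spread: *a* from 3 to 5 with *u* ≤ 3 gives 3 drops for each of 4 unit values, or 12; 12 + 32 = 44.
- After day 30, spread: nothing reaches Extensive, so Major is *a* ≥ 3, or 64 − (1 + 2 + 3) = 58. This includes all 32 sentence cells, leaving 58 − 32 = 26.

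Without the hemoglobin adjustment, exactly-one counts are 39, 47, 39 and 23 in the same row order. The overlap is still 0 in the first three rows and 32 in the last. Agreement in the last row fails once any 24-h period holds 4 U: 5 U one day and 2 U the next is Extensive.

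**Endocarditis.** Major criteria 0–2 by minor criteria 0–5 give 18 cells, with no surgical or autopsy evidence. Cells are written (major, minor).

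- Definite as printed: at least 1 major (12 cells), or 0 major and at least 3 minor (3 cells) = 15.
- Definite with *and*: 2 major (6 cells), 1 major with at least 3 minor (3 cells), and (0,5) (1 cell) = 10.
- The five differing cells are (0,3), (0,4), (1,0), (1,1) and (1,2).
- Coded possible: (0,3), (0,4), (1,1), (1,2). All 4 are also definite as printed; none is with *and*.
- The fifth differing cell, (1,0), is definite as printed and has no code in the possible rule.
- As printed, 0 of the 15 definite cells depend on the 2-major or 5-minor line, so those lines do nothing. With *and*, 4 of the 10 do: (0,5), (2,0), (2,1) and (2,2).

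**The case against.** The best reply is that the documents already show which rule governs. Section 13.0 bases event definitions on MVARC. Section 17.1.6 prints the full MVARC scale as the primary one, and Section 17.1.1 names that scale for vascular complications. For endocarditis, the possible rule is a specific coding instruction for exactly these combinations. The literal *or* makes two neighboring lines pointless, so an adjudicator would probably read past it.

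The consequences are also modest. The primary endpoint is worded "The primary safety endpoint is implant, delivery or device related serious adverse events", which uses neither grade, and no by-grade rate is a listed endpoint. Table 11-4 gives neither investigator nor sponsor a bleeding grade or Duke level to assign. Appendix 17.1 contains no composite success definition. Those supplied belong to the transapical pilot study: its procedural success uses life-threatening bleeding, and its SAP takes endocarditis by CEC code with no definite/possible split.

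The points on consequence stand and limit the size of the problem. The points on precedence do not remove it. No passage says that the 4 U sentence yields to the table, and the reading that rescues the endocarditis line is an inference, however strong. A charter could guide adjudicators, but Section 12.1 makes the protocol's definitions govern too. The CEC's minimum scope is also worded variously as deaths plus endpoint-related events (Section 5.0), primary-endpoint-related events, or clinical endpoints collected (both Section 12.1), so some events may not reach it.

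**Conclusion.** Both contradictions are in the current text and should be corrected.

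- For overt bleeds that are not life-threatening, the two Major categories share no event through day 30. They coincide only after day 30, for 4 U or more given slowly enough that no 24-h period reaches the Extensive threshold.
- All four endocarditis combinations coded as possible are also definite as printed.

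The bleeding cell counts rest on the footnote adjustment and on the reading of the 24-h limit given above. The absence of overlap through day 30 does not depend on the adjustment.

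The effect is on labels, not on the primary endpoint. The documents give no event counts, so the number of events relabelled is unknown. With up to 45 subjects, moving one subject between categories shifts a full-cohort proportion by 1/45 = 2.2 percentage points. The CEC charter, which was not supplied, may already resolve adjudicated events.

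**What to change.** 1. In Section 17.1.6, delete the 4 U sentence, or rename it as a separate transfusion category, so that one scale carries the label Major.
2. In Section 17.1.23, change *or* to *and* in the line combining 1 major with 3 minor criteria, once the sponsor confirms that this was the intent.
3. Check that the CEC charter and CRF instructions match.
4. Recheck only events whose label differs between the readings:
   - bleeds of 4 U or more, except those after day 30 with no 24-h period at the Extensive threshold;
   - bleeds under 4 U that meet the table's Major grade;
   - Duke-based endocarditis with 1 major and 0–2 minor criteria, or with 0 major and 3–4 minor.

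The cost is a two-line amendment, a document check and that limited recheck. The count labelled major bleeding may rise, as bleeds at 3 U or 3 g/dl enter, or fall, as bleeds of 4 U or more move to Extensive. The definite endocarditis count can only stay the same or fall.
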